# 1. **Objectives** (include all primary and secondary objectives)

To evaluate the effect of the PCSK9 inhibitor evolocumab on coronary endothelial function, systemic biomarkers of inflammation, and LDL cholesterol in people living with HIV (PLWH). Potential participants will be asked to undergo a screening MRI exam. Those who have evidence of coronary endothelial dysfunction on the MRI exam will receive evolocomab 420 mg sq (the dose that is approved for treatment of hypercholesterolemia) following the screening exam and again at one month. The evolocumab will be administered by the Johns Hopkins Investigational Drug Service in the HIV+ group. Repeat MRI measures of coronary endothelial function, and serum markers of endothelial function and inflammation will be obtained at one and six weeks following the first administration of evolocumab.

We will test the hypotheses that PCSK9 inhibition improves endothelial function measured non-invasively on MRI and systemic markers of inflammation at one week and six weeks after initiation of the PCSK9 antibody in PLWH.

## Primary Endpoint:

Coronary endothelial function at 1 week and 6 weeks following initiation of PCSK9 inhibitor administration; specifically, change in coronary artery cross sectional area (CSA) from that at rest to that during isometric handgrip exercise (IHE) stress (as mm^2 and as % rest) at 1 week and 6 weeks. We will be evaluating the change in endothelial function from baseline to one week and from baseline to six weeks.

## Secondary Endpoints:

- 1. Change in coronary blood flow (CBF) from rest to that during IHE stress (% rest and as ml/min) from baseline to one week and from baseline to six weeks.
- 2. Change in inflammatory markers (e.g. hsCRP, IL-6, soluble) and lipids from baseline to one week and from baseline to six weeks.

Also, the relationship between change in inflammatory markers/lipids over time and change in CEF will be quantified and compared.

2. **Background** (briefly describe pre-clinical and clinical data, current experience with procedures, drug or device, and any other relevant information to justify the research)

Increased systemic inflammation and altered lipid metabolism are two factors which play important roles in atherogenesis, both in the general population and in HIV+ individuals. Lipid abnormalities are common in HIV infected individuals and may contribute to the increased cardiovascular risk in this population. HIV infection itself and its treatment with antiretroviral therapy can alter lipid metabolism and both are associated with higher LDL cholesterol and triglyceride levels. In addition, HIV infection is marked by increased systemic inflammation, which correlates with the presence and extent of

atherosclerosis, and although systemic inflammatory markers are reduced by ART, they are not reduced to normal levels. Although statins have antiinflammatory properties and lower CV mortality in the general population, their use is often problematic in the HIV population due to frequent drug interactions and concurrent liver disease. Importantly, CV event rates remain high in HIV+ patients on statin therapy and statins alone often do not adequately suppress inflammation in many patients. Therefore, new therapies are needed to target the fundamental underlying pathophysiologic mechanisms, namely increased inflammation and altered lipid metabolism contributing to HIV-mediated atherosclerotic disease. Finally, although traditional imaging methods document the anatomic extent of coronary atherosclerosis, there was no prior safe and non-invasive way to probe the critical early mechanisms contributing to CAD, namely coronary endothelial dysfunction. However, recent advances by our research group now make it possible to non-invasively quantify coronary endothelial function (CEF) and therefore better understand the role of inflammation in coronary atherosclerosis.

# 3. Study Procedures

a. Study design, including the sequence and timing of study procedures (distinguish research procedures from those that are part of routine care).

The following are research procedures:

# HIV positive subjects:

All of the procedures described below are research procedures.

Research study of the effect of PCSK9 inhibition in 20 HIV+ subjects (with LDL cholesterol > 70 mg/dl) involving (1) subcutaneous administration of two doses of evolocumab, (420 mg, one following baseline measures of coronary endothelial function and inflammatory mediators and the second one month following the first dose). For this population, we had an FDA exemption for the off label use of evolocumab in this study, and the medication will be provided and administered by the Johns Hopkins Investigational Drug Service. HIV+ participants on stable, clinically-guided ART and meeting entry criteria will undergo baseline assessment of serum inflammatory mediators, as well as PCSK9 activity, lipids, MRI quantification of local coronary endothelial function (CEF). Those subjects with abnormal CEF, defined by an increase in coronary CSA during IHE of  $\leq$ 5% from the resting value, will qualify and enter the study. Subjects will then receive evolocumab 420 mg sg once after baseline studies and will return for repeat clinical assessment, repeat imaging, and blood draw 1 week after receiving the dose. Four weeks after receiving the first dose, they will receive a second evolocumab dose, with repeat imaging, blood draw, and safety analysis performed at week 6 after the first dose (2 weeks after the second administration). There will be a final safety assessment performed at week 10 (6 weeks after final dose given).

**Initial evaluation:** A careful history and physical examination will be performed. Blood samples will be acquired for complete blood cell count, routine chemistry panel including hepatic transaminases and creatinine, LDL and HDL cholesterol and triglycerides. Serum markers reflective of inflammation and endothelial function will include serum hsCRP, IL-6, TNF $\alpha$ , IFN- $\gamma$ , and PCSK9 level. Patients will also be tested for hepatitis C

(Hepatitis C Antibody test) if Hep C status is unknown from clinical records. If the patient is found to have positive reactivity to Hep C Antibody or is previously known to be Hep C positive (from clinical chart review using same criteria), then HCV RNA level in blood will be quantified as part of research procedure.

**MRI methods for Coronary Vasoreactivity: an index of CEF:** Patients will undergo a detailed baseline MRI study of CEF in the fasting state using MRI methodology at rest and during continuous IHE as previously described . The MRI study will be used to measure coronary cross-sectional area (CSA), coronary flow velocity (CFV), and coronary blood flow (CBF) changes in response to IHE stress (continuous isometric handgrip for 4-8 min at 30% of each subject's maximum, determined prior to entering the MRI), as previously reported.

**Fasting:** Subjects will be asked to fast after midnight and delay eating breakfast and taking morning cardiovascular medicines until after the study procedure, which will be completed by noon.

**MRI analysis**: MR images will be analyzed in blinded fashion without operator knowledge of time or treatment group for CEF (e.g. changes in CBF, CBV, and CSA) as previously validated and described . Baseline, 1-week and 6-week images will be analyzed at the same time for each subject by investigators blinded to time point of study to reduce variability and assure identical segments are analyzed at each time.

**Blood Draw and Analysis:** Blood samples will be obtained from a peripheral vein using standard venipuncture techniques and will be sent for routine chemistries (basic metabolic panel and liver function tests, CBC) and lipids. Biomarkers will be analyzed from blood specimens collected into collection tubes without anticoagulant and centrifuged within 1 hour after collection (to allow time for clotting) using a centrifuge with an integrated refrigeration system at 4°C/1000 g for 15 min and stored at -80°C. Analyses will be performed with ELISA or multiplexed ELISA including the following biomarkers of inflammation/activation/clotting: hsCRP, IL-6, TNF $\alpha$ , IFN- $\gamma$ , PCSK9 activity and CD163. In addition, comprehensive lipid panel will be measured. To minimize variability of assays of longitudinal markers, the baseline, 1- and 6-week specimens of each individual will be analyzed on the same plate.

**Safety surveillance**: Patients will undergo surveillance safety monitoring at 1 week, 4 weeks (before 2nd dose of PCSK9 inhibitor is given to HIV+ participants) and 6 weeks that will include detailed history, physical exam and complete blood count. In the HIV+ group, liver and renal function tests will additionally be performed, and there will be a 10 week safety follow up performed by phone 6 weeks after the last dose of drug is given. Members of the research team will review laboratory results from a safety standpoint.

**Follow up End-point Evaluation:** After 1 week of the first dose and at 6 weeks after the first dose (and two weeks after the second dose) of PCKS9 inhibitor administration, subjects will undergo repeat clinical evaluation, lipid and inflammatory biomarker analysis, as well as coronary MRI with the same protocols used at baseline. In terms of MRI follow up exams (at weeks 1 and 6) coronary MRI will be repeated with an identical protocol and special attention taken to interrogate the same coronary segments as those studied at

baseline, using anatomic landmarks of coronary ostia and branch vessels- as we have done in the past.

## List of study procedures (HIV+ group):

 Visit 1 (Screening Visit): includes Informed Consent, History and physical examination, vital signs (temperature, blood pressure, heart rate, weight, height), blood draw (CBC, CMP, Lipid panel, Hepatitis C Antibody Test if HCV status is unknown, HCV Quant PCR if known HCV positive, serum biomarkers of inflammation (above). MRI Screening questionnaire, cardiac MRI, If patient qualifies (based on MRI and entry criteria), the subject will receive PCSK9 inhibitor (this will be administered by a qualified study team member)

**Visit 2 (Baseline Visit)** Subject will return for medical history reviewed for changes, concomitant medications, vital signs, 1st Dose of Evolocumab will be given by study team.

**Visit 3 (1 Week after Evolocumab is started):** Subject will return for physical examinations, concomitant medications, vital signs (temperature, blood pressure, heart rate, weight), monitor for adverse events, blood draw (CBC, CMP, Lipid panel, serum biomarkers of inflammation/activation/clotting: hsCRP, IL-6, TNF $\alpha$ , IFN- $\gamma$ , PCSK9 activity), MRI Screening questionnaire, cardiac MRI

**Visit 4**: Subject will return 4 weeks after initial dose for safety assessment and to receive 2nd and final dose of evolucomab, review concomitant medications, and monitor for adverse events, measurement of vital signs (temperature, blood pressure, heart rate, weight).

**Visit 5 (6 Weeks after Evolocumab started)** Subject will return 6 weeks after initial PCSK9 inhibitor given for physical examination, concomitant medications, vital signs (temperature, blood pressure, heart rate, weight), monitor for adverse events, blood draw (CBC, CMP, Lipid panel, serum biomarkers of inflammation), cardiac MRI. Subjects will receive a phone call follow for safety assessment at week 10.

Early stopping rules

Participants who experience significant symptoms or who develop significant laboratory abnormalities will be evaluated and the scheduled second (final) study drug dose withheld. Participants who experience significant symptoms will be evaluated and those or others who develop new laboratory abnormalities will be reviewed and labs possibly repeated. If any of the following criteria are met (CBC<2000, platelets<50,000, Hct<27%, GFR <30ml/min or a >50% reduction in GFR compared to baseline values, and LFTs >3x upper limit of normal), the test would be repeated. If confirmed on repeat, the second (and final) dose of the drug would not be given (HIV+ group). If the abnormality resolves, study drugs would be given at the same or lower dose. If the abnormality does not resolve, then the case will be reviewed for discontinuation from the study. Based on the clinical status, severity of the problem, and reversal of symptoms/laboratory findings, a decision will be made as to whether the study drug (2nd and final dose) can be started under close observation (weekly surveillance) or the patient withdrawn from the study. For every study participant who withdraws, we plan to recruit an additional subject so that the overall sample size of those completing the study is close to 20-25 subjects in each group.

Participants who wish to end participation in the trial at any time may do so upon request without penalty.

b. Description of what happens to participants receiving therapy when study ends or if a participant's participation in the study ends prematurely.

Participants withdrawn from receiving the scheduled second (final) dose of evolocumab due to an adverse experience will be followed by the Investigator until the outcome is determined. Every effort will be made to follow the subject for the full study period as per the schedule of study visits.

## 4. Inclusion/Exclusion Criteria

## Inclusion Criteria (HIV positive):

- A. Participants of either gender who are  $\geq 21$  years of age (no upper age limit),
- B. HIV positive and taking stable ART (no change in ART regimen in last 3 months)
- C. Clinically controlled HIV viral load (plasma HIV RNA concentration
- ≤100copies/mL)
- D. Abnormal CEF on MRI at baseline (<5% change in CSA during IHE as compared to resting value).
- E. Lipids at screening visit: Fasting LDL-C >70 mg/dL; fasting TG<500 mg/dL F. Permission of attending physician

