of evolocumab on CEF and inflammatory mediators in subjects with abnormal CEF is the change in CSA from rest to IHE at 1 and 6 weeks. We chose to study the change in CSA because it 1.) reflects both macrovascular changes related to the endothelial-dependent IHE stressor, 2.) CEF reflected by CSA change is significantly depressed in HIV+ subjects compared to healthy subjects 3.) is reproducible over this proposed time period, and 4.) because endothelial function is an independent predictor of atherosclerotic progression and clinical events . The 6 week time was chosen to minimize confounding events occurring over longer times and because improvements in endothelial function are present in as short as 1 day to 6 weeks following the initiation of statin. We will also collect CEF measures at 1 week to evaluate safety and detect whether a short term acute CEF effect is present. Drugs that improve cardiovascular outcomes improve endothelial function in fewer than 8 weeks. An increase in the IHECSA response in subjects to approximately 30% of that of healthy subjects does not assume complete normalization of CEF in participants with evolocumab but, instead, an increase that would be biologically significant and consistent with the changes in endothelial function observed with medications shown to reduce cardiovascular outcomes. For example, a landmark study demonstrated that statins improve CEF in CAD patients to approximately half of normal/maximal responses . In studies of subjects with CAD risk factors, comparisons are typically made with baseline or placebo measures and such studies consistently show that statins and ACE inhibitors improve abnormal endothelial function by ~50% or more in CAD patients . A similar 50% increase in endothelial function was also observed in HIV+ people treated for 8 weeks with statins . Thus based on the existing literature of the impact of established cardiovascular medications (statins, ACE-I) on endothelial function and based on our observations of differences in coronary endothelial function between HIV+ and HIV- individuals (CSA increases during IHE in healthy subjects +12%±5% (mean±SD) and does not increase in HIV+ or CAD patients, change of -2%±6% (mean±SD), we propose that there will be an increase to 4% CSA change with IHE (i.e. approximately 33% of the normal 15% increase in CSA with IHE we observe in healthy individuals) in the evolocumab-administered subjects. We assume that at 6 weeks:

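### Entry requires stable ART but not stable statin or other lipid-lowering therapy, and no analysis handles a change in it, so the uncontrolled pre-post estimate can absorb a background drug effect of unknown, probably modest, size

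*Combined protocol and SAP*

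**What the plan says.** Section 4, inclusion criterion B, asks that participants be "HIV positive and taking stable ART (no change in ART regimen in last 3 months"). This is the only stability rule for background medication in the inclusion and exclusion lists. Statins, other lipid-lowering drugs and ACE inhibitors are neither excluded nor required to be unchanged, before entry or up to week 6.

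Section 5c explains why these drugs matter for the endpoint:
- Statins, timing: "improvements in endothelial function are present in as short as 1 day to 6 weeks following the initiation of statin".
- Cardiovascular drugs in general, timing: "Drugs that improve cardiovascular outcomes improve endothelial function in fewer than 8 weeks".
- Size in coronary disease: "such studies consistently show that statins and ACE inhibitors improve abnormal endothelial function by ~50% or more in CAD patients".
- Size in HIV: "A similar 50% increase in endothelial function was also observed in HIV+ people treated for 8 weeks with statins".

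The primary endpoint is the change in the CSA response to handgrip from baseline to 1 week and from baseline to 6 weeks in treated participants. No concurrent untreated comparison is specified.

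Three provisions bear on the point. Concomitant medications are listed for review at Visits 2 to 5 (at Visit 2: "medical history reviewed for changes, concomitant medications, vital signs"). On MRI days participants are to "delay eating breakfast and taking morning cardiovascular medicines until after the study procedure". Section 5c also says: "The 6 week time was chosen to minimize confounding events occurring over longer times". No section says what happens in the analysis when background therapy changes.

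**The concern.** In a single-arm pre-post design, whatever else changes between the two measurements is counted as change on evolocumab. Section 5c names a drug class that acts on the endpoint within the follow-up period. Yet a person who began a statin just before the screening MRI, or who begins one between visits, can be enrolled and stays in the primary analysis without a flag.

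The effect is not confined to CSA. A lipid-lowering change moves LDL directly. Section 2 credits statins with anti-inflammatory properties, so hsCRP can move too. Section 5 also plans to relate changes in lipids and inflammatory markers to change in endothelial function. One participant who starts a statin could move both sides of that relationship, and with about 18 people a few such points can be influential.

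The bias can run either way: a start or dose increase inflates the apparent benefit, and a stop or reduction hides some of it. Long-standing unchanged use causes no bias of this kind.

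**Working it through.** **Inputs from Section 5c.** Mean CSA response -2% at baseline and +4% on treatment, a planned effect of 6 points; SD 6%; 18 completers; 90% power, two-sided alpha 0.05; 10% dropout; 20 enrolled. Healthy response +12%. A cited statin study in coronary disease reached about half of the normal response.

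**Step 1: the plan's own figures.** Enrolment reproduces: 18 / (1 - 0.10) = 20. The power figure depends on the SD of the change, which is 6 x sqrt(2(1 - rho)) if 6% is the SD of a single measurement. By paired t-test with n = 18:
- SD of change 6 (rho = 0.5): power 97.9%.
- SD of change 8.49 (rho = 0): power 80.7%.
- Power is 90% at an SD of change of about 7.40 (rho about 0.24).

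The plan gives no rho, so n = 18 cannot be verified, but it is not shown to be wrong. That is a separate matter. It is needed here only for the standard error of the mean change: 6 / sqrt(18) = 1.41, 7.40 / sqrt(18) = 1.74, or 8.49 / sqrt(18) = 2.00 points.

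**Step 2: gain per participant who starts a drug (assumption).** The documents give no such figure for this endpoint and population, so I use a range.
- Low: 3 points, half the planned evolocumab effect.
- Middle: 6 points, equal to it.
- High: 8 points. Half of 12% is 6%, and 6 - (-2) = 8. This carries a coronary-disease result over to HIV and exceeds the effect planned for evolocumab itself.

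Section 5c also calls 15% normal. That would give 7.5 - (-2) = 9.5 points, which I regard as beyond a reasonable upper end.

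**Step 3: shift in the mean.** With k of 18 completers changing therapy and gain g, shift = k x g / 18, and share = shift / 6.

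| k | g = 3 | g = 6 | g = 8 |
|---|---|---|---|
| 1 | 0.17 (3%) | 0.33 (6%) | 0.44 (7%) |
| 2 | 0.33 (6%) | 0.67 (11%) | 0.89 (15%) |
| 3 | 0.50 (8%) | 1.00 (17%) | 1.33 (22%) |

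Every entry is below the smallest standard error in Step 1. The number k is also an assumption. For stops, the sign reverses.

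**Step 4: could this produce the planned effect?** Even at 8 points each, a 6-point shift needs 6 x 18 / 8 = 13.5, that is 14 of 18 participants.

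**Step 5: false-positive risk.** I simulated 200,000 trials per setting, with n = 18, no true evolocumab effect, gains of 3 or 6 points, and an SD of change of 6 or 7.9. The chance of a significant improvement, nominally 2.5%, is 3.0-3.8% for one starter, 3.5-5.5% for two and 4.2-7.8% for three.

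**The case against.** The case for leaving the plan alone has several parts.

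- **The window is short by design.** Section 5c gives confounding as a reason for choosing 6 weeks, and one of the two primary time points is at 1 week. This lowers the chance of a new start. It does not remove it, because the same paragraph places statin effects inside that window.
- **Criterion D screens out some early responders.** Entry requires a CSA change below 5%. By the arithmetic of Step 2, a full responder would reach +6% and fail, and any partial response is already in the baseline. The full 8 points therefore applies only if nearly all the drug effect falls after the baseline MRI. This stands and favours the lower part of the range for pre-baseline starts.
- **Recent changes may be uncommon.** Exclusion C removes people with a cardiovascular event or procedure in the past 90 days, and Section 2 describes statin use in this population as difficult. Both are plausible, but neither is a rule about medication. The second also makes stops and switches plausible.
- **Medication is already reviewed, and morning doses are delayed on MRI days.** The review yields data that no analysis uses. The delay concerns same-day dosing, not whether a drug was started.
- **It is a pilot, and the shift is smaller than its standard error.** This is true and limits the severity. But the stated purpose is to learn the effect size, so a systematic shift matters even when significance does not change.

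A reader might also infer that the protocol says ACE inhibitors act within the trial window. It does not. The 1-day-to-6-week statement concerns statins only. The sentence that names ACE inhibitors gives a size and no timing. The general statement sets a limit of 8 weeks, which is longer than follow-up. For ACE inhibitors, within-window action is an inference.

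**Conclusion.** The gap is real. The plan controls one background therapy and leaves open another that its own rationale says acts on the primary endpoint within the measurement window. With no control arm, nothing subtracts that effect.

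Its size is unknown, because the documents do not say how many participants would change therapy. On the assumptions shown (1 to 3 of 18 completers, 3 to 8 CSA points each) the mean shifts by 0.17 to 1.33 points, which is 3% to 22% of the planned 6 and less than one standard error.

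A reader might go further and infer that a positive result would be a background drug effect. The documents do not support that: about 14 of 18 participants would have to change therapy with the largest assumed gain, and nothing suggests that anyone will. This is a modest weakness that should be corrected because doing so is cheap. It does not invalidate the design.

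**What to change.** 1. **Sensitivity analysis (changes during the study).** In Section 5, pre-specify a repeat of the primary CSA analysis and of the LDL and hsCRP analyses that excludes values obtained after any start, stop or dose change of lipid-lowering or ACE-inhibitor therapy. Use the medication review already listed for Visits 2 to 5. Count changes from the screening MRI, not from the first dose, because the visit list gives no maximum interval between them. Report how many participants are affected and in which direction.
2. **Eligibility line (changes before baseline).** Add a criterion in the form of B requiring no change in these drugs before the screening MRI. The sponsor should set the interval; the 3 months already used for ART is one example. The Visit 1 list includes a history but does not name a medication review, so the current drugs and the date of the last change should be recorded at that visit.

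Both parts are needed: the eligibility line cannot prevent changes after baseline, and the sensitivity analysis does not address those before it. ACE inhibitors are included as a precaution, given the weaker basis for their timing.

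The cost is one eligibility line, one entry on the screening form, one extra analysis and a few candidates deferred. No visit or test is added, no sample-size input changes, and no participant's care is altered.
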